4.11. Secondary Analyses

4.11.1. Vital Signs

Vital sign parameters include systolic blood pressure (mmHg), diastolic blood pressure (mmHg), heart rate (bpm), pulse oximetry (%), and body temperature (°C). Vital sign assessments and the changes from baseline for each parameter will be summarized by visit for the As-Treated population. Maximal and minimal change from baseline in each parameter will also be summarized.

Weight gain and loss will be tabulated for the following categories: normal change from baseline, weight gain (5-<10%), weight gain (10-<20%) (Grade 2), weight gain (\geq 20%) (Grade 3), weight loss (5-<10%) (Grade 1), weight Loss (10-<20%) (Grade 2), and weight loss (\geq 20%) (Grade 3).

For adults (\geq 18 years of age), blood pressure parameters will be programmatically flagged for Stage 1 hypertension (systolic: \geq 140 to <160 mmHg, diastolic: \geq 90 to <100 mmHg), Stage 2 hypertension (systolic: \geq 160 mmHg, diastolic: \geq 100 mmHg), and hypotension (systolic: <90 mmHg, diastolic: <60 mmHg) [USDHHS 2003]. For children and adolescents (<18 years of age), blood pressure parameters will be programmatically evaluated based upon height- and age-specific nomograms, and categorized by percentile (<95%, \geq 95% to <99%, and \geq 99%) [USDHHS 2005]. A summary of the number and percent of subjects by systolic and diastolic blood pressure categories of <95%, \geq 95% to <99%, and \geq 99% as defined as follows.

<95%: for age <18 years old, SBP <95% and DBP <95%; for age \geq 18 years old, SBP <140 mmHg and DBP <90 mmHg.

\geq 95% to <99%: for age <18 years old, SBP \geq 95% to <99% or DBP \geq 95% to <99%; for age \geq 18 years old, SBP \geq 140 to <160 mmHg or DBP \geq 90 to <100 mmHg. In addition, none of SBP and DBP meets the following criteria of \geq 99%.

\geq 99%: for age <18 years old, SBP \geq 99% or DBP \geq 99%; for age \geq 18 years old, SBP \geq 160 mmHg or DBP \geq 100 mmHg.

Shift tables will be presented showing change in results from baseline using above <95%, \geq 95% to <99%, and \geq 99% categories.

As necessary, vital signs will be described by duration of study drug exposure, by dose, by age group, by sex, by race, by weight, and for special populations (eg, antibiotic use).

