#### **2.2.3.3.1. Phase 3 Extension Study**

Ataluren was also further tested in an international open-label, extension study in patients with nmCF (PTC124-GD-009e-CF). Subjects that completed the Phase 3 study (Study 009) were eligible for enrollment. The primary objective of this 96-week study (n=191) was to evaluate the long-term safety of ataluren in nmCF patients, at the planned daily dose level of 10-, 10-, 20-mg/kg of ataluren. Secondary objectives were to determine the long-term effect of ataluren on pulmonary function; pulmonary exacerbations, medical interventions; health-related quality of life (HRQL); general well-being; compliance with ataluren therapy; and ataluren plasma exposure. During the first 48 weeks of the trial, study assessments were performed at clinic visits every 4 to 8 weeks, depending upon the type of outcome measure. During the final 48 weeks of the trial, study assessments were performed at clinic visits every 8 to 16 weeks, depending upon the type of outcome measure. The results of this study are pending.

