##### *Tertiary*

- Change from baseline to end of treatment in spirometric performance as measured by FVC and FEF25-75
- Change from baseline to end of treatment in body weight and BMI

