#### **14.1.2. Inclusion of Minors**

Inclusion of both children and adults in this protocol is appropriate and necessary. Based on past experience in multiple randomized clinical trials [[Fuchs 1994](#), [Ramsey 1999](#), [Saiman 2003](#), [Elkins 2006](#)], including the double-blind study of ataluren in nmCF [[Rowe 2012](#)], there is strong precedence for this approach. The benefit-risk ratio is enhanced by inclusion of only children with FEV1 values ≤ 90% of predicted, weighting enrollment toward those who are already experiencing CF-related pulmonary compromise. In addition, this ratio is enhanced by the known severity of the disease phenotype in patients with CF caused by nonsense mutations [[Shoshani 1992](#), [Cystic Fibrosis Genotype-Phenotype Consortium 1993](#), [Kerem 1996](#), [de Gracia 2005](#), [McKone 2006](#)], the generally favorable safety profile of ataluren, and the limited

population of patients with nonsense-mutation-mediated disease (10% of the total CF population).

Inclusion of children as well as adults will allow an understanding of how age-dependent disease characteristics may affect treatment outcomes. A total of 65 (86.7%) patients <18 years of age completed Study 009 and are eligible for this open-label extension study. Participation of these younger patients in this extension study will allow further exploration of the influence of age on safety and efficacy outcomes. Study participants will now be at least 9 years of age, enhancing the ability of participants to reliably perform protocol procedures [Loeb 2008] and will have nomogram data describing %-predicted FEV1 values [Wang 1993].

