#### **14.2.9.3. Weight/Body Mass Index**

Patients with CF are generally underweight compared to healthy individuals of the same gender and age [Rabin 2004]. Assessment of body weight and BMI during the course of this Phase 3 study is planned. While changes in these parameters are quite nonspecific, they constitute simple-to-assess outcomes of general well-being.

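### The SAP grades weight gain with no age limit, so growth in minors can be tabulated as Grade 2 or 3; it also drops relative FVC change without listing the departure (minor, descriptive tables only)

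*SAP*

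**What the plan says.** **Weight.** SAP 4.11.1 introduces the table with "Weight gain and loss will be tabulated for the following categories: normal change from baseline". The categories are percentages of the subject's own baseline weight. The list begins "normal change from baseline, weight gain (5-<10%), weight gain (10-<20%) (Grade 2), weight gain" and continues with a gain of 20% or more as Grade 3, followed by three graded bands for loss. No age restriction is given. The next paragraph of the same section does separate minors for blood pressure: "For children and adolescents (<18 years of age), blood pressure parameters will be programmatically evaluated" using nomograms specific to height and age. The section closes by allowing vital signs to be described by age group, among other factors, where necessary.

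Minors are expected. Protocol 14.1.2 states "Study participants will now be at least 9 years of age" and "A total of 65 (86.7%) patients <18 years of age completed Study 009 and are eligible". Weight is also a tertiary efficacy variable (Protocol 3.2: "Change from baseline to end of treatment in body weight and BMI"), and Protocol 14.2.9.3 says of the population: "Patients with CF are generally underweight compared to healthy individuals of the same gender and age". SAP 4.12.2 reports change in CDC weight and height percentiles for subjects under 18 at baseline.

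**FVC.** Protocol 11.4.7.1 applies the FEV1 methods to FVC and FEF25-75. Protocol 11.4.6.2.1 defines those methods for FEV1: relative change in %-predicted, with height taken at the same visit, by-visit descriptive summaries and paired t-tests. SAP 4.11.3 keeps absolute and relative change in %-predicted FEV1. SAP 4.12.1 plans absolute change in FVC and nothing else. SAP Section 6, which records changes from the protocol, does not mention FVC. SAP Section 1 says that the SAP prevails where the two documents conflict.

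**The concern.** A fixed percentage of baseline weight means one thing in an adult and another in a child who is growing. The SAP uses age-specific limits for blood pressure, ECG heart rate (4.11.2) and creatinine (Table 2), but not for weight gain, the quantity most directly driven by growth. There is no control arm, so a reader of the graded table alone cannot tell growth from abnormal gain. The same gain in a child could also appear as a favourable tertiary result in 4.12.2 and as a Grade 2 or 3 finding in 4.11.1.

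For FVC, absolute change alone does not put children and adults on a common scale. If the quantity is volume, growth can offset a loss measured against predicted. The protocol's cross-reference to the FEV1 methods would have dealt with this, and a reader who checks Section 6 would not learn that it had been dropped.

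**Working it through.** **Weight: inputs.** Cut-offs of 10% and 20% (SAP 4.11.1) and visit weeks (Protocol Table 3). The documents give no growth rates, so a constant annual rate g is assumed. The section states no time point for the weight table; the figures apply to whichever visit is tabulated. The plan has no figure of its own to reproduce.

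Years on study: y = weeks × 7 / 365.25. Annual gain needed to reach cut-off c: g = (1 + c)^(1/y) − 1.

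| Visit | y | Grade 2 (c = 0.10) | Grade 3 (c = 0.20) |
|---|---|---|---|
| Week 48 | 0.920 | 10.9% a year | 21.9% a year |
| Week 96 | 1.840 | 5.3% a year | 10.4% a year |
| Week 192 | 3.680 | 2.6% a year | 5.1% a year |

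For Week 96: 1.1^(1/1.840) − 1 = 0.053 and 1.2^(1/1.840) − 1 = 0.104.

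In the other direction, with an assumed range of 3 to 12% a year, cumulative gain (1 + g)^y − 1 is 2.8 to 11.0% at Week 48 and 5.6 to 23.2% at Week 96. At Week 48 only the top of that range touches Grade 2 and none of it reaches Grade 3. At Week 96 it runs from ungraded to Grade 3.

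The Week 192 row is hypothetical. SAP 2.1 ends the study on 2 March 2017. Reaching Day 1344 by then needs a first dose by about late June 2013, and the documents give no enrolment dates.

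**Weight: how many subjects.** The number of minors enrolled is not given. The protocol counts 65 completers of Study 009 under 18. Of the extension open to completers it says "The primary objective of this 96-week study (n=191) was to evaluate the long-term safety of ataluren in nmCF patients", so there were at least 191 completers. The share of minors in the pool is therefore at most 65/191 = 34.0%. If about 70 enrol in that proportion (assumption), that is at most 0.340 × 70 = 23.8, or about 24. If the 65 were counted by age in Study 009, were evenly spread over ages 6 to 17 and are now three years older (assumptions), 65 × 9/12 = 48.75 are still minors, and 48.75/191 × 70 = 17.9, or about 18. Each child graded adds 1/70 = 1.4 percentage points to a row.

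**FVC: the texts side by side.**

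| Place | FEV1 | FVC |
|---|---|---|
| Protocol 11.4.6.2.1 and 11.4.7.1 | Relative change in %-predicted, by-visit summaries, paired t-tests | Same methods |
| SAP 4.11.3 and 4.12.1 | Absolute and relative change in %-predicted | Absolute change only |
| SAP Section 6 | t-test removal listed | Not mentioned |

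Section 6 also lists removal of the time-of-withdrawal analysis and the FEF25-75 summary. Even if the removal of the FEV1 t-test is read across to FVC, the loss of relative change is still unlisted.

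Whether SAP 4.12.1 means volume has to be inferred, because no unit is stated. SAP 5.1 supports the inference: it names FEV1 and %-predicted FEV1 as separate quantities, but FVC only once. If it is volume, relative volume change = (1 + r)(1 − d) − 1, where r is growth in the predicted value and d is the relative fall against predicted. The fall is hidden when r = 1/(1 − d) − 1. Borrowing the two Study 009 FEV1 falls at Week 48 purely for scale, d = 2.5% gives r = 2.6% and d = 5.5% gives r = 5.8%.

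**The case against.** The strongest reply on weight is that growth is already handled. SAP 4.11.1 allows description by age group, SAP 4.12.2 gives CDC percentile change for those under 18, and SAP 4.1 promises by-subject listings. This stands as mitigation. But the age-group description is optional and leaves the cut-offs unchanged, and the percentiles are a separate output, so the graded rows would still be misread on their own.

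A reader might infer that growth would inflate adverse event counts or severity grades, or trigger safety actions. The documents do not support that. Adverse events are graded by the investigator (SAP 4.10.1), abnormal findings become events only if they need intervention or further investigation (Protocol 9.1.1), and weight is not in SAP Table 2. Nor is it a contradiction for weight to appear in both a safety and an efficacy table.

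On FVC, the tertiary endpoint as worded asks only for change from baseline, and absolute change meets it. The SAP also takes precedence, so the operative analysis is clear. Both replies stand. A reader might infer an unresolved conflict between the documents; what remains is a departure missing from the list. Nor do the documents support the inference that growth would turn a falling cohort FVC into an apparent improvement. That would need the unit, the age mix, baseline volumes and growth, none of which they give.

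**Conclusion.** Both points hold, as minor points about descriptive tables. Followed as written, SAP 4.11.1 can count ordinary growth as Grade 2 or 3 weight gain. The firm result is the threshold: 5.3% a year for Grade 2 and 10.4% a year for Grade 3 by Week 96, at a constant rate. How many children would cross it cannot be stated, because growth rates, the number of minors enrolled and the actual follow-up are not in the documents. It would be too strong to say that most minors will be graded, or to rely on the Week 192 thresholds. The weight-loss rows are not inflated by growth and are not in question.

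For FVC, relative change is missing from the SAP and the departure is not listed in Section 6. The masking by growth is conditional on FVC being volume, which is inferred. No error rate or sample size is involved, and the primary adverse event and laboratory analyses and the %-predicted FEV1 analysis are untouched.

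**What to change.** **Weight (SAP 4.11.1).** Always present the weight-gain rows separately for subjects under 18 and 18 or over at baseline, using the age groups already defined in SAP 4.6. Add a footnote directing readers to the CDC weight-percentile change in 4.12.2 for the younger group. Keep minors in the table, since dropping them would lose the count of large individual gains. Leave the weight-loss rows for all ages.

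**FVC (SAP 4.12.1).** Add absolute and relative change in %-predicted FVC by visit, parallel to 4.11.3, and state the unit of any change in FVC itself. Name the reference equations, because Protocol 11.4.6.2.1 assigns them for FEV1 only. That text also leaves females from 16 up to and including 18, and males aged exactly 18, without an equation, so the wording must cover every age. If only absolute change is kept, list the departure and its reason in Section 6.

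**Cost.** SAP wording and programming before database lock, with no new data. Age, sex, height, weight and spirometry are already collected, and the age split and CDC percentiles are already planned. The one real decision is the choice of FVC equations: Protocol 14.2.9.1 says the spirometry system normalises for gender, age and height, but not for which parameters.

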4.11.2. Electrocardiographic Analyses

The assessments and change from baseline in electrocardiographic (ECG) parameters (e.g., RR, PR, QRS, QT, heart rate, QTcB, and QTcF) will be summarized by visit for the As-Treated population. Maximal and minimal change from baseline in each parameter will also be summarized.

Standard ECG intervals will be determined. The QT interval will be corrected by both the Bazett's and Fridericia's method as follows:

$$\text{Bazett's: } QTcB = QT / (RR)^{1/2}$$

$$\text{Fridericia: } QTcF = QT / (RR)^{1/3}$$

The QTc data obtained by using the Bazett and Fridericia corrections will be categorized separately into the following classifications and summarized by visit:

- QTc interval >450 msec and ≤480 msec
- QTc interval >480 msec and ≤500 msec
- QTc interval >500 msec

The change of the QTc values obtained by using the Bazett and Fridericia corrections will also be categorized separately as follows and summarized by visit:

- QTc interval increases from baseline by >30 msec and ≤60 msec
- QTc interval increases from baseline by >60 msec

QTc data will be presented in shift tables from baseline to each visit based on the categories: <450 msec, 450-480 msec, >480 msec.

The number and percentages of subjects with abnormal ECG parameter assessments will be tabulated by visit. Below list the abnormal criteria for the parameters:

- Heart rate > 140 bpm or < 50 bpm for age > 17 (or <60 for age 13-17, or <75 for age 6-12 and/or increase/decrease by > 30 bpm for heart rate;
- PR > 250 and/or increase by > 50 ms for PR interval;
- QRS > 120ms and/or increase by > 20 ms for QRS duration;
- QT, QTcB or QTcF > 500 ms and/or increase by > 60 ms for QT interval and its corrections.

Shift tables for the interpretation of the 12-lead ECG results (“normal”, “abnormal, clinically insignificant”, “abnormal, potentially clinically significant”) will be presented by treatment group to show the change in results from baseline (“normal”, “abnormal, clinically insignificant”, “abnormal, potentially clinically significant”) to each visit (“normal”, “abnormal, clinically insignificant”, “abnormal, potentially clinically significant”).

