#### **8.2.9. 12-Lead ECG**

A 12-lead electrocardiogram (ECG) will be obtained at Screening (Visit 1), Week 16 (Visit 3), Week 32 (Visit 4), Week 48 (Visit 5), Week 64 (Visit 6), Week 80 (Visit 7), Week 96 (Visit 8), Week 112 (Visit 9), Week 128 (Visit 10), Week 144 (Visit 11), Week 160 (Visit 12), Week 176 (Visit 13), Week 192 (Visit 14/End of Treatment), and Week 196 (Visit 15 - Post-Treatment Visit; 4 weeks post discontinuation of study drug). The central reading provided by a certified vendor will serve as the official study result. Starting in the second year of the study, after Week 56, ECGs will be read locally at investigational sites and interpreted for clinical significance. The findings will be captured in source documents and within the CRF.

Additional ECGs may be performed at any time during the study as clinically indicated at the discretion of the investigator. However, the PTC medical monitor must be informed via e-mail that an additional ECG was obtained.

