5.2. Analysis Visits

Analysis visits are the scheduled visits in the protocol, unless specified otherwise. They are not derived via visit window mapping. Baseline is derived as noted in Section 5.1. Final Visit is derived as the last non-missing on-treatment visit during the study for each subject and included into the by-visit summary analyses. Early termination visit should also be derived as the visit right after the non-missing scheduled visit. For example, if the subject discontinued after Week 8, the early termination visit should be derived as Week 16.

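### SAP 4.11.2 counts QTc and ECG outliers only by visit, so no planned summary table gives the number of subjects with an outlier at any time on treatment; separately, the QTc shift table has no group above 500 msec

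*SAP*

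**What the plan says.** SAP 4.11.2 plans five threshold- or category-based ECG outputs, and all of them are tied to visits:

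- QTcB and QTcF levels are "categorized separately into the following classifications and summarized by visit". The three groups start at "QTc interval >450 msec and ≤480 msec" and end at "QTc interval >500 msec".
- QTc increases above 30 and above 60 msec "will also be categorized separately as follows and summarized by visit".
- For the QTc shift, "QTc data will be presented in shift tables from baseline to each visit based on the categories: <450 msec, 450-480 msec, >480 msec".
- For the limits on heart rate, PR, QRS, QT and QTc, "The number and percentages of subjects with abnormal ECG parameter assessments will be tabulated by visit". The QT and QTc limits there are above 500 msec and/or an increase above 60 msec.
- The shift in overall ECG interpretation also runs from baseline to each visit.

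SAP 5.2 adds that "Analysis visits are the scheduled visits in the protocol, unless specified otherwise". It does not use visit windows, and its Final Visit row takes the last on-treatment value, not the worst. Protocol 8.2.9 allows ECGs outside the schedule: "Additional ECGs may be performed at any time during the study as clinically indicated at the discretion of the investigator".

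Three planned items do cross visits: the summary of maximal and minimal change in each ECG parameter (SAP 4.11.2), the number of subjects with an abnormal ECG reported as a treatment-emergent adverse event (SAP 4.10.1), and the by-subject listings for each CRF module (SAP 4.1).

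**The concern.** Change in ECG measurements is a named secondary safety endpoint (Protocol 3.2, SAP 2.3.2). For rare QTc outliers, a safety reader first wants to know how many subjects ever had one. A set of by-visit rows does not answer that, because it cannot separate one subject with persistent prolongation from several subjects with one episode each. Elsewhere the SAP uses the rule that would answer it: adverse events (4.10.1) and the laboratory safety monitoring parameters (4.10.2) are counted once per subject at the worst grade. ECG data get no such rule.

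An ECG taken between visits because of a clinical concern may also enter no by-visit count.

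The cut-points are a second, independent matter. The frequency and shift tables of the same section use different QTc groups, and the shift table has no group for the level that the section itself calls abnormal.

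**Working it through.** The plan gives no figure to reproduce here: the sample size is not based on power (SAP 2.4) and the analyses are descriptive (SAP 4.2). The check has two parts.

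**1. What the by-visit rows allow**

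Inputs:
- About 70 subjects (SAP 2.4).
- On-treatment post-baseline ECGs at Weeks 16, 32, ..., 192 (Protocol Table 3 and 8.2.9), so 192/16 = 12 visits. The Week 196 follow-up ECG is post-treatment and is left out.
- The study was to be terminated early, with ongoing subjects discontinued (SAP 2.1). The documents do not say how many visits subjects reached.

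Let n_v be the number of subjects beyond a limit at visit v. The number E ever beyond it at a scheduled visit satisfies

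max(n_v) ≤ E ≤ min(N, sum of n_v).

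The lower end means that the same subjects recur at each visit; the upper end means that they differ every time. The by-visit rows contain nothing that narrows the range.

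Assume one subject above the limit at every visit, with N = 70:

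| On-treatment ECG visits | Each row shows | E, lowest | E, highest |
|---|---|---|---|
| 12 (full schedule) | 1/70 = 1.4% | 1 (1.4%) | 12 (12/70 = 17.1%) |
| 4 (assumed effect of termination) | 1/70 = 1.4% | 1 (1.4%) | 4 (4/70 = 5.7%) |

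If every row is zero, E over scheduled visits is zero and nothing is lost. The gap matters only when outliers appear.

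**2. Can another planned output supply E?**

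- *Maximal change.* SAP 4.1 requires the maximum for continuous summaries, so this table shows whether anyone exceeded +60 msec. It does not give the number who did, and it says nothing about the absolute 500 msec limit.
- *Adverse-event count.* Protocol 9.1.1 makes an ECG abnormality an adverse event only if it needs intervention or further investigation beyond a repeat test, and not if it belongs to a clinical event already reported. The count follows reporting, not thresholds.
- *Listings.* E can be counted by hand from them, but it is not a planned summary.

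**3. The two sets of QTc groups**

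| QTc (msec) | Frequency table | Shift table |
|---|---|---|
| 450 | no group | 450-480 |
| 451 to 480 | >450 to ≤480 | 450-480 |
| 481 to 500 | >480 to ≤500 | >480 |
| 501 or more | >500 | >480 |

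Values of 481 and 530 msec share a shift cell, so a move to above 500 msec cannot be read from that table. The difference at exactly 450 msec is minor. If QTc is taken as normal with mean 405 to 420 and SD 15 to 20 msec, recorded in whole msec (an assumption; the documents give no distribution), about 0.03% to 0.65% of ECGs fall on that value.

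**The case against.** A reader might infer that the number of subjects ever affected is never reported. The documents do not support that. The listings hold the data, and with about 70 subjects and few outliers a hand count is feasible. The adverse-event table is a subject-level ECG count over the whole treatment period, although it rests on reporting.

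A reader might also infer that the mismatched cut-points cause the missing count, or that values above 500 msec appear nowhere. Neither follows. The shift table is by visit too, so matching cut-points alone would still give no any-time count. The by-visit level table isolates values above 500 msec; what the shift table loses is their cross-classification by baseline.

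Other points on this side have weight:

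- The endpoint is worded as change from baseline, and Protocol 11.4.6.1 itself plans summaries by visit. No contradiction in the plan is being corrected.
- The outlier counts used above are hypothetical. Protocol 15.3 reports no ECG safety concerns in earlier trials, and early termination shortens the series of visits.
- For additional ECGs, Protocol 8.2.9 expressly asks only for an e-mail to the medical monitor. Whether their interval values are in the database is not stated, so it would go too far to say that such data will be lost or that they are certainly available.
- A crude any-time proportion rises with the number of ECGs attended, and it pools readings that are central at first and local after Week 56.

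These points limit the size of the concern and shape the remedy. They do not supply the missing summary.

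**Conclusion.** The point holds as a gap in the planned summary tables. Every threshold-based ECG and QTc output is by visit, and none counts a subject once at the worst on-treatment value. With the assumed counts, identical rows fit 1.4% to 17.1% of subjects over 12 visits, or 1.4% to 5.7% over 4. These ranges show what the tables leave open. They do not predict outliers, and nothing in the documents suggests that a QTc effect is being concealed.

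The missing group above 500 msec in the shift table is a separate and real defect. The 450 msec boundary is close to editorial. Because the listings allow manual recovery and the endpoint is secondary and descriptive, this is a worthwhile improvement and no threat to the study's conclusions.

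**What to change.** Amend SAP 4.11.2 before database lock, as SAP 1 allows:

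1. Add an any post-baseline on-treatment row to the QTcB and QTcF level tables, the QTc change tables and the abnormal-ECG table. Count each subject once, at the worst value over scheduled ECGs and any unscheduled ECGs recorded in the database.
2. Use one set of QTc groups in both the frequency and shift tables: ≤450, >450 to ≤480, >480 to ≤500, and >500 msec.
3. Add a baseline-to-worst column to the QTc shift table.
4. Report the number of ECGs per subject beside the new rows, and note that readings are central at first and local after Week 56.

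The cost is SAP wording and one extra row or column per existing table. It needs no new data collection, since unscheduled ECGs enter only where already recorded.
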